5.1.3.6 PAP Pressure Measurements from Baseline through 12 Months

[REDACTED]

5.1.3.7 NT-proBNP and BNP at Baseline, 6 Months, and 12 Months

[REDACTED]

[REDACTED]

5.1.3.8 HFHs at 12 months post-implantation compared to HFHs 12 months prior to implantation

[REDACTED]

5.2 GUIDE-HF Single Arm

5.2.1 GUIDE-HF Single Arm - Primary Endpoint

5.2.1.1 Hypothesis

The primary endpoint is a composite of recurrent HFHs or emergency department/hospital outpatient observation visits for intravenous diuretic therapy or all-cause mortality at 12 months post-implantation (same as for the Randomized Arm), to be compared between subjects with an elevated NT-proBNP (or BNP) only and subjects with a prior HFH only. To demonstrate equivalence of outcomes between elevated NT-proBNP (or BNP) only subjects and prior HFH only subjects, the following hypothesis will be tested for the Composite Endpoint at 12 months:

H_{0a} : $\ln[\text{HR for Composite Endpoint (Elevated NT-proBNP (or BNP) Only vs. Prior HFH Only)}] \leq -0.2877$

H_{0b} : $\ln[\text{HR for Composite Endpoint (Elevated NT-proBNP (or BNP) Only vs. Prior HFH Only)}] \geq 0.2877$

H_1 : $-0.2877 < \ln[\text{HR for Composite Endpoint (Elevated NT-proBNP (or BNP) Only vs. Prior HFH Only)}] < 0.2877$

Where \ln is the natural log

[REDACTED]

[REDACTED]

[REDACTED]

5.2.1.2 Analysis Methods

The hypothesis will be tested at the 5% significance level.

[REDACTED]

[REDACTED]

[REDACTED]

Abbott

Study Document No.: [REDACTED]

Study Name: CardioMEMS™ GUIDE-HF IDE

Statistical Analysis Plan

[REDACTED]

[REDACTED]

Propensity Stratification Method

[REDACTED]

[REDACTED]

[REDACTED]

[REDACTED]

[REDACTED]

[REDACTED]

[REDACTED]

[REDACTED]

[REDACTED]

Abbott

Study Document No.: [REDACTED]

Study Name: CardioMEMS™ GUIDE-HF IDE

Statistical Analysis Plan

[REDACTED]

[REDACTED]

[REDACTED]

[REDACTED]

5.2.1.3 Sample Size

[REDACTED]

[REDACTED]

[REDACTED]

[REDACTED]

[REDACTED]

[REDACTED]

[REDACTED]

[REDACTED]

[REDACTED]

[REDACTED]

[REDACTED]

5.2.1.4 Analysis Population

The analysis population will include enrolled subjects having a successful implant with elevated NT-proBNP (or BNP) level only and subjects with a prior HFH only. Subjects with both elevated NT-proBNP (or BNP) and prior HFH will not be included in the analysis for the primary endpoint.

5.2.1.5 Poolability Analysis

[REDACTED]

5.2.1.6 Sensitivity Analysis

[REDACTED]

[REDACTED]

[REDACTED]

5.2.1.7 Subgroup Analysis

5.2.2 GUIDE-HF Single Arm: Secondary Safety and Effectiveness Endpoints

The secondary effectiveness endpoints of the GUIDE-HF Single Arm are HFH + HFH Equivalents and the comparison of annualized rate of recurrent HFH at 12 months post-implantation to the annualized rate of recurrent HFH in the 12 months prior to implantation. In addition, the individual components of the primary endpoint will each be evaluated as descriptive secondary effectiveness endpoints: HFH at 12 months post-implantation, emergency department/hospital outpatient observation visits for intravenous diuretic therapy at 12 months post-implantation, and all-cause mortality at 12 months post-implantation. [REDACTED]

The analysis population for the secondary effectiveness endpoints will include subjects enrolled into the Single Arm and successfully implanted regardless of NT-proBNP (or BNP) and HFH history unless otherwise noted.

The secondary safety endpoint of the GUIDE-HF Single Arm is freedom from DSRCs at 12 months post-implantation. The analysis population for the secondary safety endpoint will include subjects enrolled in the Single Arm (i.e. with an attempted implant, whether successful or unsuccessful).

5.2.2.1 HFH + HFH Equivalents at 12 months post-implantation

5.2.2.1.1 Hypothesis

To demonstrate equivalence of HFH + HFH Equivalents between elevated NT-proBNP (or BNP) only subjects and prior HFH only subjects, the following hypothesis will be tested for HFH + HFH Equivalents at 12 months:

$H_{0a}: \ln[\text{HR for HFH + HFH Equivalents (Elevated NT-proBNP (or BNP) Only vs. Prior HFH Only)}] \leq -0.2877$

$H_{0b}: \ln[\text{HR for HFH + HFH Equivalents (Elevated NT-proBNP (or BNP) Only vs. Prior HFH Only)}] \geq 0.2877$

$H_1: -0.2877 < \ln[\text{HR for HFH + HFH Equivalents (Elevated NT-proBNP (or BNP) Only vs. Prior HFH Only)}] < 0.2877$

Where \ln is the natural log

[REDACTED]

[REDACTED]

[REDACTED]

5.2.2.1.2 Analysis Methods

[REDACTED]

5.2.2.1.3 Missing Data Sensitivity Analyses

[REDACTED]

5.2.2.1.4 Sample Size

[REDACTED]

[REDACTED]

5.2.2.2 HFHs at 12 months post-implantation compared to HFHs 12 months prior to implantation

5.2.2.2.1 Hypothesis

The secondary endpoint will be evaluated using the following hypothesis:

H_0 : HR for annualized HFH at 12 months (Rate at 1 year post-implant to Rate at 1 year pre-implant) ≥ 1

H_1 : HR for annualized HFH at 12 months (Rate at 1 year post-implant to Rate at 1 year pre-implant) < 1

[REDACTED]

[REDACTED]

[REDACTED]

5.2.2.2.2 Analysis Population

This secondary endpoint will be evaluated for the cohort of subjects enrolled into the Single Arm following successful implantation regardless of NT-proBNP (or BNP) and HFH history.

5.2.2.2.3 Analysis Methods

[REDACTED]

The null hypothesis will be rejected if the upper limit of the 1-sided, 97.5% CI for the HR of Post-Implant to Pre-Implant is less than 1.

5.2.2.2.4 Sample Size

[REDACTED]

5.2.2.2.5 Subgroup Analysis

The following 3 subgroups will be used for descriptive analyses (rates, hazard ratio and 2-sided 95% CI for the HR) of this secondary endpoint:

- a) elevated NT-proBNP only
- b) prior HFH only and
- c) both elevated BNP and HFH.

[REDACTED]

[REDACTED]

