4.1.3 GUIDE-HF Single Arm

The GUIDE-HF Single Arm is a prospective, multi-center, single-arm clinical trial of the CardioMEMS™ HF System in North America in NYHA Class III HF patients, with either elevated NT-proBNP (or BNP) and/or a prior HFH. After screening procedures and signing the Informed Consent Form, subjects will

[REDACTED]

[REDACTED]

complete baseline assessments. Within 60 days of consent, subjects will receive a CardioMEMS™ HF System. Subjects will be considered enrolled in the Single Arm once all entry criteria are met, informed consent is provided, and implantation of the CardioMEMS™ PA Sensor is attempted. Safety information and adverse events (AEs) will be reported (per section 8.2) for all enrolled subjects. However, subjects will only contribute towards the sample size and primary, secondary effectiveness, and descriptive endpoint analyses following successful implantation. Subjects will upload PA pressure information daily, and receive HF management guided by PA pressure information.

The GUIDE-HF Single Arm will include approximately 2600 subjects (following successful implantation) at approximately 140 sites. Each subject will be followed for 12 months, with follow-up visits at 6 and 12 months.

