4.4.1 Inclusion Criteria

To participate in this clinical trial and receive a CardioMEMS™ HF System implant, subjects must meet all of the following inclusion criteria:

1. Diagnosis and treatment for HF (regardless of LVEF) for > 90 days prior to the date of consent:
 - a. Subjects should be on stable, optimally titrated medical therapy for at least 30 days, as recommended according to current AHA/American College of Cardiology (ACC) guidelines as standard-of-care for HF therapy in the United States, with any intolerance documented.
2. **GUIDE-HF Randomized Arm Only:** NYHA Class II, III or IV HF symptoms documented within 30 days prior to consent.
3. **GUIDE-HF Single Arm Only:** NYHA Class III HF symptoms documented within 30 days prior to consent.
4. HFH within 12 months prior to consent and/or elevated NT-proBNP (or BNP) within 30 days prior to consent defined as:
 - a. Subjects with LVEF ≤ 40%: NT-proBNP ≥ 1000 pg/mL (or BNP ≥ 250 pg/mL).
 - b. Subjects with LVEF > 40%: NT-proBNP ≥ 700 pg/mL (or BNP ≥ 175 pg/mL).
 - c. Thresholds for NT-proBNP and BNP (for both LVEF ≤ 40% and LVEF > 40%) will be corrected for BMI using a 4% reduction per BMI unit over 25 kg/m²
5. ≥ 18 years of age
6. Chest circumference of < 65 inches, if BMI is > 35 kg/m²
7. Written informed consent obtained from subject

8. Willing and able to upload PA pressure information and comply with the follow-up requirements

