6.2 GUIDE-HF Single Arm

6.2.1 Primary Endpoint

The primary endpoint is a composite of recurrent HFHs or emergency department/hospital outpatient observation visits for intravenous diuretic therapy or all-cause mortality at 12 months post-implantation (identical to the Randomized Arm primary endpoint). The two subject groups to be compared are a) subjects having elevated NT-proBNP (or BNP) but without having a HFH in the year prior (i.e., **elevated NT-proBNP (or BNP) only subjects**) and b) subjects having a HFH in the year prior but without elevated NT-proBNP (or BNP) (i.e., **prior HFH only subjects**). The analysis population of the GUIDE-HF Single Arm primary endpoint will include subjects enrolled into the Single Arm and successfully implanted with either **elevated NT-proBNP (or BNP) only** or **a prior HFH only**. Subjects with both elevated NT-proBNP (or BNP) and a prior HFH will not be included in the analysis for the primary endpoint.

To demonstrate equivalence of outcomes between subjects with elevated NT-proBNP (or BNP) only and those with prior HFH only, the following hypothesis will be tested:

H_{0a} : $\ln[\text{HR for Composite Endpoint (Elevated NT-proBNP (or BNP) Only vs. Prior HFH Only)}] \leq -0.2877$

H_{0b} : $\ln[\text{HR for Composite Endpoint (Elevated NT-proBNP (or BNP) Only vs. Prior HFH Only)}] \geq 0.2877$

H_1 : $-0.2877 < \ln[\text{HR for Composite Endpoint (Elevated NT-proBNP (or BNP) Only vs. Prior HFH Only)}] < 0.2877$

Where \ln is the natural log

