3.1.2 GUIDE-HF Single Arm

The GUIDE-HF Single Arm is a prospective, multi-center, single-arm clinical trial of the CardioMEMS™ HF System in North America in NYHA Class III HF patients, with either elevated NT-proBNP (or BNP) and/or a prior HFH. After signing the Informed Consent Form and confirmation of meeting all entry criteria for the Single Arm, subjects will complete baseline assessments. Within 30 days of consent, subjects will receive a CardioMEMS™ HF System. Subjects will be considered enrolled in the Single Arm once all entry criteria are met, informed consent is provided, and implantation of the CardioMEMS™ PA Sensor is attempted. However, subjects will only contribute towards the endpoint analysis following successful implantation. Subjects will upload PA pressure information daily, and receive HF management guided by PA pressure information.

The GUIDE-HF Single Arm will enroll approximately 2600 subjects at approximately 140 sites. Each subject will be followed for 12 months, with follow-up visits at 6 and 12 months.

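### SAP 5.2.2.2.5 plans a post/pre-implant HFH hazard ratio in a subgroup selected for having no HFH in the prior year, so the ratio is either not finite or set by the consent-to-implant gap

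*SAP*

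**What the plan says.** The endpoint is a secondary effectiveness endpoint of the Single Arm. SAP 5.2.2.2.1 sets the effect measure as "HR for annualized HFH at 12 months (Rate at 1 year post-implant to Rate at 1 year pre-implant", so the pre-implant rate is the denominator. SAP 5.2.2 describes that denominator as the "annualized rate of recurrent HFH in the 12 months prior to implantation".

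For subgroups, SAP 5.2.2.2.5 says: "The following 3 subgroups will be used for descriptive analyses (rates, hazard ratio and 2-sided 95% CI for the HR) of this secondary endpoint". The list is (a) "elevated NT-proBNP only", (b) prior HFH only, and (c) both. No exception for (a) is visible. The text straight after the list is redacted, as is the method paragraph in SAP 5.2.2.2.3.

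Protocol 6.2.1 defines group (a) as "subjects having elevated NT-proBNP (or BNP) but without having a HFH in the year prior". The SAP label omits BNP; I read it as the same group, which SAP 5.2.3 lists among three pre-defined groups.

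The windows have different anchors:

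- **Eligibility** runs back from consent: "HFH within 12 months prior to consent and/or elevated NT-proBNP (or BNP) within 30 days prior to consent defined as" (protocol 4.4.1).
- **The endpoint** runs back from implantation.
- **The longest gap between them** is 60 days in protocol 4.1.3 ("Within 60 days of consent, subjects will receive a CardioMEMS™ HF System") and 30 days in SAP 3.1.2 ("Within 30 days of consent, subjects will receive a CardioMEMS™ HF System").

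**The concern.** A before/after ratio needs events before. Subgroup (a) is formed by requiring that there were none, so the selection rule fixes the denominator and the ratio says nothing about pressure-guided care.

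The subgroup matters. Class III patients hospitalised for heart failure in the previous year are already within the approved indication (protocol 3.1.2). The Single Arm is meant to support extending it to Class III patients with raised peptide (protocol 6.3, SAP 5.9), so group (a) is the newly added Class III population. As the visible text stands, its planned output is either not estimable or a ratio well above 1. Any decision to suppress the ratio, add a continuity correction or move the pre-implant window would then be taken after the data had been seen.

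**Working it through.** The visible text gives no expected rate, ratio or subgroup size for this endpoint, so there is no figure to reproduce. The check follows the definitions through.

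**Inputs from the documents.** Ratio = post-implant rate / pre-implant rate, one year each (SAP 5.2.2.2.1). Group (a) has no HFH in the prior year (protocol 6.2.1). Maximum gap is 60 days (protocol 4.1.3) or 30 days (SAP 3.1.2).

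**Assumptions, not in the documents.** Subgroup size 300 to 1000; post-implant rate 0.1 to 0.4 HFH per patient-year; equal exposure before and after.

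**Case 1: no pre-implant HFH counted.** This arises if the prior year ends at implant (a gap HFH then moves the subject to group (c)), if gap HFHs are not recorded, or if none occur.

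- Point estimate: x/0, not finite. The log hazard ratio does not exist, so neither does a Wald interval.
- Model fit, as an illustration because the planned model is redacted: a Poisson regression on 120 post-implant against 0 pre-implant events does not converge. The log ratio is 11.4, 21.4, 26.4 and 43.4 after 10, 20, 25 and 50 iterations, and its standard error goes from 16 to 2×10^7.
- Exact conditional interval for x post-implant and 0 pre-implant events: p_L = 0.025^(1/x), lower limit = p_L/(1 − p_L), upper limit infinite.
  - x = 30 (300 × 0.1): p_L = 0.884, lower limit 7.6.
  - x = 120 (600 × 0.2): lower limit 32.0.
  - x = 400 (1000 × 0.4): lower limit 107.9.
  - The lower limit exceeds 1 when p_L > 0.5, that is x > ln(0.025)/ln(0.5) = 5.3, so from six events on.

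The exact interval therefore excludes 1 on the side of harm at any plausible event count, whatever the device does.

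**Case 2: gap HFHs are counted and the subject stays in group (a).** This requires that the prior year ends at consent. Only the gap part of the pre-implant year can then contain events. With a constant rate r and no device effect:

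expected ratio = r / (r × gap/365) = 365/gap, with gap in days. If gaps vary, the mean gap takes its place.

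| Gap (all subjects) | No device effect | True 50% reduction | True reduction needed for a ratio below 1 |
|---|---|---|---|
| 60 days | 365/60 = 6.1 | 3.0 | above 1 − 60/365 = 84% |
| 30 days | 365/30 = 12.2 | 6.1 | above 1 − 30/365 = 92% |

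Shorter gaps make it larger: 365/15 = 24.3. With 600 subjects at 0.2 per year and no device effect, the counts would be about 120 against 20 (ratio 6.0, exact 95% CI 3.7 to 10.2) for a 60-day gap, and 120 against 10 (12.0, 6.3 to 25.7) for a 30-day gap.

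The non-finite ratio and the 365/gap factor do not depend on the assumed sizes and rates; the counts and intervals do.

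**The case against.** **Redaction.** Redacted blocks follow the subgroup list, which is where a rule for group (a) would sit, and the estimation method is redacted too. A reader might infer that the SAP has no rule for a zero denominator. The documents do not support that; only that none is visible. Even so, the visible sentence promises a ratio and interval for all three groups and needs a qualification.

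**No interval at all.** A reader might infer that a confidence interval is impossible. It is not: an exact interval exists, with an infinite upper limit. What fails is the point estimate and any Wald interval.

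**Exactly zero.** A reader might infer that the denominator is exactly zero by definition. That holds only if the prior-year window ends at implant. Protocol 6.2.1 does not say where it ends, eligibility is anchored at consent, and protocol 5.10.4 adjudicates prior HFHs back from baseline.

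**The 6.1 and 12.2.** These are not forecasts. The 60 and 30 days are ceilings, and the figures need gap HFHs to be captured without moving the subject to another group. Capture is unclear: protocol 8.2 starts safety reporting at attempted implant, protocol 8.2.1 asks for prior HFHs back from baseline, and Table 2 marks reportable events at baseline only as applicable. This objection stands against treating the numbers as predictions. It does not rescue the ratio, because without those conditions case 1 applies.

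**Small consequence.** The analysis is descriptive, and rates are promised alongside the ratio, so a careful reader would see a near-zero pre-implant rate beside it. This limits the damage but is no reason to plan an uninformative ratio.

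**Conclusion.** The concern holds in this form: the visible text of SAP 5.2.2.2.5 plans a post/pre hazard ratio with a 95% CI in a subgroup whose definition removes the pre-implant events, apart from any in the consent-to-implant gap. With none counted, the ratio is not finite and an exact interval is bounded only below, above 1. With gap events counted under the stated conditions, the ratio reflects the gap: 6.1 or 12.2 at the two ceilings with no device effect, and more for shorter gaps.

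A reader might go further and infer that this threatens the Single Arm's success or the primary comparison. The documents do not support that. Success rests on the primary endpoint (SAP 5.7), which compares post-implant outcomes between groups (SAP 5.2.1.1) and does not use this ratio. Nor would a large ratio in group (a) be evidence of harm. The issue is one misleading descriptive output, worth correcting before analysis because of the population it describes.

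**What to change.** In SAP 5.2.2.2.5, for subgroup (a):

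- drop the post/pre hazard ratio and its interval;
- report the annualised post-implant HFH rate with a 95% CI, together with the pre-implant HFH count;
- state that a post/pre ratio is not interpretable because the group is selected on having no HFH in the year prior.

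This wording is safer than saying that the count is zero by definition, since gap events may be recorded. Keep rates, hazard ratio and CI for (b) and (c) as planned. If a redacted passage already handles group (a), the visible sentence should point to it.

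The cost is a sentence or two in the SAP. The primary endpoint, the whole-cohort test of this endpoint and data collection are unchanged. The only output given up is a ratio that would not inform on the device.

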5.2.2.3 Individual Components of the Primary Endpoint

5.2.2.3.1 HFH at 12 months post-implantation

[REDACTED]

5.2.2.3.2 HFH Equivalents at 12 months post-implantation

[REDACTED]

5.2.2.3.3 All-Cause Mortality at 12 months post-Implantation

[REDACTED]

5.2.2.4 Secondary Safety Endpoint: Freedom from DSRC over 12 Months Post-Implantation

The secondary safety endpoint of freedom from DSRC is defined as an adverse event that is related or possibly related to the system (wireless pressure sensor or external electronics) and has at least one of the following characteristics:

- is treated with invasive means (other than intramuscular medication or a right heart catheterization which is used for diagnostic purposes)
- results in the death of the subject
- results in the explant of the device

The frequency of DSRCs and the frequency and proportion of subjects having freedom from DSRCs at 12 months post- implantation will be reported for the overall cohort as well as for each pre-defined subject group.

5.2.3 **GUIDE-HF Single Arm: Descriptive Endpoints**

Each of the following descriptive endpoints will be evaluated for the full cohort, as well as for each of the three pre-defined subject groups separately: a) elevated NT-proBNP (or BNP) only subjects, b) prior HFH only subjects, and c) both elevated NT-proBNP (or BNP) and a prior HFH subjects. These descriptive endpoints will be reported using these descriptive statistics: n, mean, median, standard deviation, minimum and maximum for continuous variables; frequency and percent for categorical variables; annualized rates for time-to-event variables (or time-between-events variables for recurrent-data endpoints).

5.2.3.1 EQ-5D-5L at 6 and 12 months

[REDACTED]

[REDACTED]

[REDACTED]

Abbott

Study Document No.: [REDACTED]

Study Name: CardioMEMS™ GUIDE-HF IDE

Statistical Analysis Plan

5.2.3.2 KCCQ-12 at 6 and 12 months

[REDACTED]

5.2.3.3 6MHW test at 6 and 12 months

[REDACTED]

5.2.3.4 Cardiovascular Mortality at 12 Months Post-Implantation

[REDACTED]

5.2.3.5 All-Cause Hospitalizations at 12 Months Post-Implantation

[REDACTED]

5.2.3.6 Frequency of Subject PA Pressure Uploads through 12 Months

[REDACTED]

[REDACTED]
[REDACTED]

[figure not shown]
Abbott

Study Document No.: [REDACTED]

Study Name: CardioMEMS™ GUIDE-HF IDE

Statistical Analysis Plan

5.2.3.7 Frequency of Clinician Review of Uploads through 12 Months

[figure not shown]
5.2.3.8 HF Medication Changes through 12 Months

5.2.3.9 PAP Pressure Measurements from Baseline over 12 Months

5.2.3.10 BNP and NT-proBNP at Baseline, 6 Months and 12 Months

5.3 Sensitivity Analyses to Evaluate Possible Impact of COVID-19 for Randomized Arm

5.3.1 Primary Endpoint

[REDACTED]

[REDACTED]

[REDACTED]

[REDACTED]

5.3.2 Secondary Effectiveness Endpoints

5.3.2.1 HFH + HFH Equivalents at 12 months post-implantation

[REDACTED]

5.3.2.2 EQ-5D-5L at 6 and 12 Months

[REDACTED]

5.3.2.3 KCCQ-12 at 6 and 12 Months

[REDACTED]

[REDACTED]

[REDACTED]

5.3.2.4 6MHW test at 6 and 12 Months

[REDACTED]

5.3.3 Descriptive Secondary Effectiveness Endpoints (Individual Components of the Primary Endpoint):

5.3.3.1 HFH at 12 months post-implantation

[REDACTED]

5.3.3.2 HFH Equivalents at 12 months post-implantation

[REDACTED]

5.3.3.3 All-Cause Mortality at 12 months post-Implantation

[REDACTED]

[REDACTED]

5.4 Sensitivity Analyses to Evaluate Possible Impact of COVID-19 Single Arm

5.4.1 Primary Endpoint

[REDACTED]

[REDACTED]

[REDACTED]

[REDACTED]

5.4.2 Secondary Effectiveness Endpoints

5.4.2.1 HFH + HFH Equivalents at 12 months post-implantation

[REDACTED]

5.4.2.2 HFHs at 12 months post-implantation compared to HFHs 12 months prior to implantation

[REDACTED]

5.4.3 Descriptive Secondary Effectiveness Endpoints, Individual Components of the Primary Endpoint:

5.4.3.1 HFH at 12 months post-implantation

[REDACTED]

[REDACTED]

5.4.3.2 HFH Equivalents at 12 months post-implantation

[REDACTED]

5.4.3.3 All-Cause Mortality at 12 months post-Implantation

[REDACTED]

5.4.4 **Descriptive Endpoints**

5.4.4.1 EQ-5D-5L at 6 and 12 Months

[REDACTED]

5.4.4.2 KCCQ-12 at 6 and 12 Months

[REDACTED]

5.4.4.3 6MHW test at 6 and 12 Months

[REDACTED]

[REDACTED]

5.5 **Overall Sample Size**

The sample size required for evaluation of the Randomized Arm and Single Arm primary endpoints is approximately 3600 (1000 for the Randomized Arm and 2600 for the Single Arm).

[REDACTED]

[REDACTED]

